7.4 Data summary

Data will be collected on case report forms for each participant at each visit and doubleentered into a secure study database. A quality check of data will occur after the first five records and prior to analysis, looking for out-of-range values and inconsistent data. The study statistician will conduct additional quality checks prior to data analyses including consistency between rounds of data entry, checking for duplicate entries, truncation of data, out-of-range values, inconsistent data and amount of missing data. Data discrepancies will be resolved and documented prior to data analysis. Missing data will not be imputed. After quality checks have been completed, a final database will be created with proper formatting and any appropriate mathematical algorithms applied including change from randomization visit (Visit 3).

Descriptive summaries will be generated for all demographic and clinical variables by study visit and treatment group including number, mean, median, standard deviation, minimum and maximum for continuous variables and number and percent for categorical variables. Summaries for change from randomization visit will also be generated. The number and screening/baseline characteristics of withdrawn participants will be recorded.

Subgroups for analyses may include treatment group, time point/study visit, age group and sex. A significance level of 0.05 will be used throughout with no adjustment for multiplicity. Normality will be tested throughout using the Shapiro-Wilk test. All analyses will be conducted on the final dataset in SAS version 9.3 or higher.

7.4.1 Summary of primary outcome data

The primary objective of this experimental protocol is to assess cognitive tolerability of mirabegron while treating OAB symptoms in patients with PD and CI. The hypothesis is that mirabegron will not impact cognitive impairment. The goal is to demonstrate equivalent cognitive impairment prior to and following treatment with mirabegron as well as change compared to the placebo group. To assess this primary objective, a test of equivalence will be performed using the two one-sided tests approach on change from visit 3 to visit 7 in MoCA total score within groups as well as between the two groups. Normality will be assessed by the Shapiro-Wilk test and the appropriate t-test or non-parametric alternative will be used. The equivalence range will be set at (-2, 2).

Other measures of cognitive impairment will follow similar analyses, but will not be considered the primary endpoint. Equivalence ranges will be determined for each measure based on available literature prior to data analysis.

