Descriptive statistics will be performed. The primary group for analysis will consist of all subjects who received at least one dose during the double-blind placebo-controlled phase. Analyses will compare change from randomization (visit 3) to end of treatment (visit 7). Tests of equivalence will be performed on primary, secondary and exploratory outcomes, with significance level of p<.05.

Study Procedures:

Refer to the Study Schedule/Flowchart, below.

Number of Subjects: 30 (20 active treatment, 10 placebo group).

Eligibility criteria:

INCLUSION CRITERIA:

- 1. Aged 25-80 at screening. Subjects older than 80 will be allowed at the discretion of the PI.
- 2. Ambulatory (defined as able to ambulate at least 10 meters, with or without assistance).
- 3. Clinical Diagnosis of PD based on the United Kingdom Brain Bank diagnostic criteria for PD.
- 4. At baseline visit (Visit 2) patients must have:
 - a. At least 8 micturitions per 24 hours and

- b. At least 3 urgency episodes per 3-day diary.
- 5. A MoCA score between 19 and 28 (inclusive) at screening. For those on cognitive enhancers (donepezil, rivastigmine, memantine, galantamine) a MoCA score between 19 and 29 (inclusive) at screening.
- 6. Provide informed consent to participate in the study and understand that they may withdraw their consent at any time without prejudice to their future medical care.
- 7. Be cognitively capable, in the opinion of investigator, to understand and provide such informed consent.
- 8. Be cognitively capable to complete the required questionnaires and assessments, OR have a care partner who is willing and capable to assist them in the completion of these tasks.
- 9. Be on a stable regimen of antiparkinson's medications at least 30 days prior to screening, and be expected to remain on a stable dose for the duration of the study.
- 10. If taking cognitive enhancers (donepezil, rivastigmine, memantine, galantamine), must be on stable dose at least 30 days prior to screening, and be expected to remain on a stable dose for the duration of the study.

EXCLUSION CRITERIA:

- 1. Known or suspected alcohol or substance abuse in the preceding 12 months.
- 2. Women who are pregnant or breastfeeding.
- 3. Women of childbearing potential (WOCP) who are not using at least one method of contraception.
- 4. Patients with severe renal impairment ($CL_{cr} \le 29 \text{ mL/min}$, or eGFR ≤ 29 mL/min/1.73 m²), or moderate or severe hepatic impairment (Child-Pugh classes B or C).

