3.3 Inclusion Criteria

- 1. Aged 25-80 at screening. Subjects older than 80 will be allowed at the discretion of the PI.
- 2. Ambulatory (defined as able to ambulate at least 10 meters, with or without assistance).
- 3. Clinical Diagnosis of PD based on the United Kingdom Brain Bank diagnostic criteria for PD.²⁸
- 4. At baseline visit (Visit 2) patients must have:
 - a. At least 8 micturitions per 24 hours and
 - b. At least 3 urgency episodes per 3-day diary.
- 5. A MoCA score between 19 and 28 (inclusive) at screening. For those on cognitive enhancers (donepezil, rivastigmine, memantine, galantamine) a MoCA score between 19 and 29 (inclusive) at screening.
- 6. Provide informed consent to participate in the study and understand that they may withdraw their consent at any time without prejudice to their future medical care.

- 7. Be cognitively capable, in the opinion of investigator, to understand and provide such informed consent.
- 8. Be cognitively capable to complete the required questionnaires and assessments, OR have a care partner who is willing and capable to assist them in the completion of these tasks.
- 9. Be on a stable regimen of antiparkinson's medications at least 30 days prior to screening, and be expected to remain on a stable dose for the duration of the study.
- 10. If taking cognitive enhancers (donepezil, rivastigmine, memantine, galantamine), must be on stable dose at least 30 days prior to screening, and be expected to remain on a stable dose for the duration of the study.

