3.9.3 Randomization (Visit 3; Day 0)

Randomization visit procedures will aim at collecting data that will be utilized as baseline measures for the statistical analysis for primary and secondary outcomes, and exploratory analyses.

- Concomitant medications
- Adverse events
- Study drug compliance
- Vital signs, weight, height, and orthostatics
- OABO
- 3-day VD assessment
- PPBC
- CQ
- UPDRS-6
- MoCA
- Map Search
- Hopkins Verbal Learning Test (HVLT)
- Trail Making Test (TMT) parts A and B
- Beck Anxiety Inventory (BAI)
- Beck Depression Inventory version II (BDI-II)
- Epworth Sleepiness Scale (ESS)
- Parkinson Fatigue Scale (PFS)
- Parkinson's Impact Scale (PIMS)
- Study drug dispense

At the conclusion of the randomization visit, subjects will be randomized in a double-blind fashion in a ratio of 2:1 to mirabegron 25 mg daily vs. placebo. Study drug will be administered in the form of 1 mirabegron 25 mg extended release matching placebo tablet daily (placebo arm) or 1 mirabegron 25 mg extended release tablet daily (active treatment arm). Thus all subjects will continue to receive 1 tablet daily. Sufficient study drug will be dispensed to last until Visit 6.

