7.4.2 Summary of efficacy data

The first secondary objective of this project is to assess the efficacy of mirabegron for treating OAB symptoms in PD with CI. The hypothesis is that participants in the

treatment group will experience improved OAB symptoms compared to placebo group. As this is a superiority objective, a 2-sample t-test or the Mann-Whitney-Wilcoxon test will be used as appropriate to determine significant differences between treatment groups on change in OABQ subscale scores from visit 3 to visit 7. Other measures of OAB symptoms (including PPBC and the average daily values from the diary) will follow similar analyses.

The rest of the secondary objectives are to assess efficacy of mirabegron in PD and the impact of mirabegron on other non-motor symptoms in PD including health related quality of life and excessive daytime sleepiness in PD patients with OAB symptoms and CI. The related hypotheses are that mirabegron will not impact these non-motor symptoms. The goal is to demonstrate equivalent non-motor symptoms prior to and following treatment with mirabegron as well as change compared to the placebo group. Tests of equivalence will be performed using the two one-sided tests approach on change from visit 3 to visit 7 in related variables within groups as well as between the two groups. Equivalence ranges will be determined for each measure based on available literature prior to data analysis.

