7.4.3 Summary of exploratory data

The exploratory objectives are to assess effects of mirabegron on orthostatic changes in blood pressure, depressive and anxiety symptomatology, excessive salivation, constipation and PD motor symptom severity in PD patients with OAB symptoms and CI. The related hypotheses are that mirabegron will not impact these symptoms. The goal is to demonstrate equivalent symptoms prior to and following treatment with mirabegron as well as change compared to the placebo group. Tests of equivalence will be performed using the two one-sided tests approach on change from visit 3 to visit 7 in related variables within groups as well as between the two groups. Equivalence ranges will be determined for each measure based on available literature prior to data analysis.

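### Between-arm tests use unadjusted Visit 3 to Visit 7 change; ANCOVA on the Visit 3 score, with the primary method fixed in advance, can narrow the interval at a small, stated cost

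*Combined protocol and SAP*

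**What the plan says.** Section 7.4.1 applies two one-sided tests (TOST) with range (-2, 2) "on change from visit 3 to visit 7 in MoCA total score within groups as well as between the two groups". The method is then chosen from the data: "Normality will be assessed by the Shapiro-Wilk test and the appropriate t-test or non-parametric alternative will be used". Section 7.4 extends this to every analysis: "Normality will be tested throughout using the Shapiro-Wilk test".

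For OAB efficacy, Section 7.4.2 says "a 2-sample t-test or the Mann-Whitney-Wilcoxon test will be used as appropriate", again on change. Section 7.4.3 does the same for the exploratory outcomes, which include salivation, constipation and motor severity: "Tests of equivalence will be performed using the two one-sided tests approach on change from visit 3 to visit 7 in related variables".

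No section names a covariate or a regression model. Yet Section 3.9.3 says of Visit 3: "Randomization visit procedures will aim at collecting data that will be utilized as baseline measures for the statistical analysis". Section 7.1 sets 20 versus 10 for feasibility, without a calculation. Sections 7.3 and 7.4.6 exclude withdrawn subjects from the analysis and do not replace them after randomization.

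**The concern.** A change score is the Visit 7 score minus exactly 1 times the Visit 3 score. Least squares would use a slope of rho x SD7/SD3, where rho is the correlation between visits. If that is well below 1, raw change carries avoidable noise from Visit 3 and passes part of any chance baseline difference into the treatment contrast. With at most 10 placebo patients, the between-arm interval is the weakest part of the primary analysis, and its width is a main product of a pilot.

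Separately, the Shapiro-Wilk step decides after the data are seen whether (-2, 2) is applied to a mean difference or to a location shift. The plan does not say which sample is tested for normality, or which rank procedure follows.

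**Working it through.** **Plan's own figure.** Section 7.1 gives N = 30 with no power, SD or correlation. Only 10 + 20 = 30 and the 2:1 ratio can be checked, and both agree.

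**Inputs.** From the documents: 20 versus 10, margin 2, alpha 0.05. Assumed: 0.05 per one-sided test (a 90% CI), true difference 0, bivariate normal scores, Visit 3 SD 2.5, k = SD7/SD3 of 0.8, 1.0 or 1.2, and rho 0.5 to 0.9. A wider spread at Visit 7 (k above 1) is plausible because entry restricts the score: "A MoCA score between 19 and 28 (inclusive) at screening" (29 for users of cognitive enhancers).

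**Degrees of freedom.** The t-test has 30 - 2 = 28 and ANCOVA has 30 - 3 = 27. The one-sided 5% t quantile goes from 1.7011 to 1.7033 (+0.13%).

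**Variance ratio, ANCOVA to change, N = 30.** k²(1 - rho²)/(1 + k² - 2k·rho) x 27/26, where 27/26 = 1 + 1/(N - 4) is the expected cost of chance imbalance in the covariate.
- k = 1 reduces to (1 + rho)/2 x 27/26. At rho 0.5 this is 0.75 x 1.038 = 0.78; at 0.7, 0.88; at 0.9, 0.99. Break-even is rho = 52/27 - 1 = 0.926.
- k = 1.2, rho 0.8: 1.44 x 0.36/(2.44 - 1.92) = 0.997, and x 1.038 = 1.035. ANCOVA is less precise for rho between 0.69 and 0.91, that is, slopes of 0.83 to 1.10.
- k = 0.8: ANCOVA is more precise at every rho.

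**Between-arm TOST power, change to ANCOVA, 20 versus 10** (40,000 simulated trials per cell):

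| k | rho 0.5 | rho 0.7 | rho 0.8 | rho 0.9 |
|---|---|---|---|---|
| 1.0 | 30 to 48% | 66 to 74% | 88 to 90% | 99.5 to 99.6% |
| 1.2 | 15 to 21% | 50 to 50% | 75 to 73% | 97 to 96.5% |
| 0.8 | 42 to 77% | 75 to 93% | 91 to 98.5% | 99.6 to 100% |

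Mean 90% CI width at k = 1 goes from 3.26 to 2.88 points (rho 0.5), 2.53 to 2.38 (0.7) and 2.06 to 2.00 (0.8). With 16 versus 8 analysed (assumed 20% withdrawal) and k = 1, power goes from 15 to 30% (rho 0.5) and 50 to 58% (0.7). At k = 1.2, rho 0.8, it goes from 60 to 56%.

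**Chance imbalance.** The SD of the Visit 3 mean difference is 2.5 x √(1/20 + 1/10) = 0.97 points. With k = 1 and rho 0.5, each point moves the raw-change contrast by 1 - 0.5 = 0.5, against a margin of 2.

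**Error rate.** At a true difference of -2 (20 versus 10), equivalence is declared in 3.0-5.0% of trials with change and 3.7-5.2% with ANCOVA.

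**Pretest.** Take integer-rounded normal changes with SD 1.5/2/2.5 and test normality per arm. Shapiro-Wilk rejects in 43/25/19% of trials, but the verdict differs from the t-test's in only 1.6/3.0/2.7% if the rank method is a Mann-Whitney TOST on shifted data. The choice of rank method matters more. With integer scores capped at 30, SD 3 and rho 0.8, the t-test gives 67% power. The pretest rule gives 66.5% with the shifted Mann-Whitney test, but 55% with a Hodges-Lehmann 90% interval required to lie strictly inside (-2, 2).

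**Why the Hodges-Lehmann rule fails here.** MoCA changes are integers, so a limit often equals the margin. For 20 versus 10 and SD 1.5/2/2.5, a limit falls exactly on -2 or +2 in 44/66/58% of trials. Read as an open range, power is 55/17/3%. Read as closed, false equivalence at a true difference of -2 is 21/15/12%. The shifted Mann-Whitney TOST gives 88/55/26% power and 4-5% error.

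**The case against.** Unadjusted change is an acceptable prespecified analysis, and this is a feasibility-sized pilot with no power target to miss. The size of the gain rests wholly on an assumed SD, rho and k. Across 54 cells (SD 2, 2.5 or 3; k 0.8, 1 or 1.2; rho 0.4 to 0.9) the power change runs from -2.4 to +41 points. The largest gains come from k = 0.8, which nothing in the documents favours. At k = 1.2, the direction that restricted entry suggests, the median gain is only 1.0 point, and 9 of 18 cells gain under 1 point or lose. At k = 1 the median gain is 9 points. Where the gain is large, power often stays poor.

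Most of this stands. It limits the claim to a conditional gain in precision, but leaves the trade favourable: the loss exceeds 0.5 points in 4 of the 54 cells.

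A reader might go further and infer that the planned test is biased or invalid, or that the pretest inflates type I error. Neither follows. Randomization makes the change contrast unbiased on average, and the error rates above stay at or near 5%. A reader might also infer that ANCOVA costs only one degree of freedom. It also carries the 27/26 factor, and it loses power when the slope is near 1.

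**Conclusion.** The point holds as an inexpensive improvement that should be made, not as a flaw that invalidates the analysis. The plan leaves a collected baseline unused in the between-arm tests and lets the data choose the primary method. With equal SDs at the two visits, ANCOVA gives a material gain for rho up to about 0.7, a small one at 0.8 and none at 0.9. If the true slope is near 1, it costs about 2 points of power, or about 3.5 with 16 versus 8. All of these sizes rest on assumed inputs. The within-group equivalence tests are unaffected.

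The reason to drop the pretest is that the estimated quantity should be fixed before the data are seen. Its effect on verdicts is small if the alternative is the shifted rank test.

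Two gaps in outcome handling belong with this change. Section 7.4.3 assigns TOST on change to salivation (one item scored 0-4) and constipation (a count of criteria), which are ordinal or count-like. And Table 1 and Section 3.9.3 do not schedule full UPDRS at Visit 3, so its planned Visit 3 change cannot be computed.

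**What to change.** Amend Sections 7.4 to 7.4.3 before unblinding:
- For MoCA, the OABQ subscales and the other approximately continuous scales measured at Visit 3, make the between-arm analysis an ANCOVA of change on arm and Visit 3 score. Using the Visit 7 score as outcome gives the same arm effect, so the change endpoint is kept. Report the adjusted difference with a 90% CI against the equivalence margin, or a 95% CI for superiority.
- Remove Shapiro-Wilk as the selector of the primary method.
- For MoCA, name the Mann-Whitney TOST on data shifted by -2 and +2 as the sensitivity analysis, in place of any Hodges-Lehmann interval compared with (-2, 2).
- Specify rank or ordinal methods for PPBC, UPDRS-6 and the constipation items.
- Use the screening value as baseline for full UPDRS.
- State whether sex, which Section 7.2 aims to balance, enters the model. Adding it costs a second degree of freedom (26, t quantile 1.7056).

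The cost is SAP wording and one SAS procedure, with no new data. The statistical cost is one degree of freedom, the expected variance factor of about 27/26, and the small power loss given above when the slope is near 1.

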During the 2-week run-in placebo period all subjects will receive placebo tablets matching the 25 mg mirabegron extended release tablets. During the first two weeks of the double-blind placebo-controlled phase, subjects will be randomized to either 25 mg extended release mirabegron or matching placebo (2:1 ratio). During the following 10 weeks of the double-blind placebo-controlled phase, subjects tolerating treatment without side-effects will be escalated to 50 mg mirabegron (two 25 mg mirabegron extended release tablets) or matching placebo (two placebo tablets); subjects experiencing side-effects that do not preclude continuation of the study will continue at the dosage level of one 25 mg extended release mirabegron tablet or matching placebo daily. Subjects who have escalated to 50 mg mirabegron or matching placebo and experience side-effects at that level, will be allowed one dose reduction to 25 mg mirabegron or matching placebo.

Depending on dose level, one or two tablets will be administered daily, with or without food, swallowed whole with water; chewing, crushing or dividing is not allowed.

Primary Endpoint:

Relative mean change to the MoCA score between randomization visit (Visit 3) and week 14 visit (Visit 7).

Table 1. Schedule of Activities:

VISIT/PROCEDURE:	Screening Visit	Baseline Visit	Randomizati on	Low dose phase	Dose escalation	High dose phase	End of TX / Early Term	Follow-up / Week 16
	V 151t					•		
Visit number	1	2	3	4 phone	5	6	7	8
Visit time	week -4 to -6	week -2	day 0	day 7	day 14	day 42	day 84	day 98
Informed consent	X							
Inclusion/Exclusion criteria	X							
Past history/demographic	X							
Neurological and physical exam	X	X			X		X	X
Urologic exam	X *				X*			X*
Cystoscopy	X*							
Concomitant medication	X	X	X	X	X	X	X	X
Adverse events		X	X	X	X	X	X	X
Study drug compliance			X	X	X	X	X	
UPDRS	X				X		X	X
Vital signs (includes weight, height and orthostatics)	X	X	X		X		X	X
ECG	X				X		X	
Pregnancy test (for WOCP)	X							X
Urinalysis	X*				X*		X	X*
Blood samples (safety)	X						X	
OABQ	X		X		X	X	X	
3-day VD training and concordance	X							
3-day VD assessment		X	X		X	X	X	
PVR	X*				X*			X*
PPBC		X	X		X	X	X	X
CQ			X				X	
UPDRS-6			X				X	
MoCA	X		X				X	
Map Search			X				X	
HVLT			X				X	
TMT A and B			X				X	
BAI			X				X	
BDI-II			X				X	
ESS			X				X	
PFS			X				X	
PIMS			X				X	
Drug dispense		X	X			X		

^{*} Procedures performed during the urology visit

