1.3.2 Selection of primary outcome

Although it may seem unusual for a clinical trial on OAB, a global cognitive measure was selected as the primary outcome measure, since the essence of this trial lies in demonstrating cognitive tolerability of this medication in PD patients with overactive bladder. The Montreal Cognitive Assessment²³ (see Appendix II) was chosen as a concise, comprehensive, and sensitive global measure of cognitive dysfunction, with proven accuracy in PD.²⁴ In this patient group, it has been demonstrated to be superior to the Minimental State Examination (MMSE) and equivalent to the more extensive and time consuming Scales for Outcomes in Parkinson disease-Cognition (SCOPA-COG)²⁵ in detecting mild cognitive impairment. The instrument takes approximately 10 minutes to administer, and contains tests of the cognitive domains of attention and concentration, executive function, memory, language, visuoconstructional skills, conceptual thinking, calculations, and orientation. Three versions are available to improve test-retest reliability and reduce practice effects. It is scored 0-30, with higher scores reflecting better cognitive function. Normative data have been developed and cut-off scores are available. A score of <26 is considered a cutoff for both mild cognitive impairment and dementia

In this protocol we use the MoCA both as an outcome measure and as an inclusion and exclusion criterion. The purpose of this study is to examine the cognitive tolerability of mirabegron in PD patients with some impaired cognitive function (CI), yet not having cognitive dysfunction of an extent that would a) interfere with the subject's ability to participate in study procedures and provide informed consent or b) affect the subject's

ability to control bodily functions and thus interfere with measures of efficacy. Additionally there is a mounting evidence in the literature that the cut off of 26 may be too strict, with 66% of subjects in a recent population based study falling below this suggested cutoff.²⁷

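### MoCA is measured twice before randomisation, but the between-arm equivalence test uses only the unadjusted change from Visit 3 and so forgoes precision from data already collected

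*Combined protocol and SAP*

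**What the plan says.** Table 1 schedules the MoCA at Visits 1, 3 and 7. Section 1.3.2 gives it two roles: "In this protocol we use the MoCA both as an outcome measure and as an inclusion and exclusion criterion". Inclusion criterion 5 (section 3.3) requires "A MoCA score between 19 and 28 (inclusive) at screening", with an upper limit of 29 for subjects on cognitive enhancers. A screening score therefore exists for everyone who is randomised.

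Section 3.9.3 takes the analysis baseline from Visit 3: "Randomization visit procedures will aim at collecting data that will be utilized as baseline measures for the statistical analysis for primary and secondary outcomes". Section 7.4.1 then applies two one-sided tests "on change from visit 3 to visit 7 in MoCA total score within groups as well as between the two groups", with an equivalence range of (-2, 2). It adds that "the appropriate t-test or non-parametric alternative will be used" after a normality check. No covariate is named, and the screening MoCA has no role in the analysis. Section 7.1 fixes the sample at 20 and 10 for feasibility, without a sample size calculation.

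**The concern.** The MoCA is a 30-point test with measurement error. Change from one Visit 3 score carries that error in full into each subject's outcome. A second score taken before randomisation holds further information on the same subject's level, and it can be used even when the analysis already adjusts for Visit 3.

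Precision decides this trial's primary conclusion, because the 90% CI for the treatment difference must lie within 2 points of zero. The sample size is fixed, and section 7.3 excludes withdrawn participants, so the analysed number can only fall. Better use of data already collected is one of the few ways left to narrow the interval. Both scores precede randomisation, so entry selection and practice effects at Visit 1 do not bias the comparison between arms.

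**Working it through.** The plan states no power, SD or correlation, so there is no figure of its own to reproduce.

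**Inputs from the documents:** n = 20 and 10; margin 2 points; significance level 0.05, taken as 0.05 for each one-sided test (a 90% CI). **Assumed:** equal variance s² at the three visits; correlations a = r(V1,V3), b = r(V3,V7), c = r(V1,V7); SD of the Visit 3 to Visit 7 change equal to 2; true difference 0.

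**Planned interval.** Half-width = t(0.95; 28 df) × 2 × √(1/20 + 1/10) = 1.701 × 2 × 0.387 = 1.32 points.

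**Variances, in units of s²:**
- Change from Visit 3: 2(1 − b).
- Change from the mean of Visits 1 and 3: 1 + (1 + a)/2 − (b + c).
- ANCOVA on Visit 3: 1 − b².
- ANCOVA on Visits 3 and 1: 1 − (b² + c² − 2abc)/(1 − a²).

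*All correlations equal to r.* The first two become 2(1 − r) and 1.5(1 − r), so averaging cuts change-score variance by 25% at any r. At r = 0.7 the four values are 0.600, 0.450, 0.510 and 0.424. The two-covariate model is then 29% below the planned change score (1 − 0.424/0.600) and 17% below ANCOVA on Visit 3 alone (1 − 0.424/0.510).

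*Visit 1 less predictive, a/b/c = 0.80/0.80/0.75.* Averaging gives 1 + 0.90 − 1.55 = 0.35 against 0.40, a cut of 12.5%. The second covariate gives 1 − 0.2425/0.36 = 0.326 against 0.360, a cut of 9%.

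*a/b/c = 0.85/0.80/0.70.* Averaging gives 1 + 0.925 − 1.50 = 0.425 against 0.40, which is 6% worse than planned. The second covariate gives 1 − 0.178/0.2775 = 0.3586 against 0.360, a cut of only 0.4%.

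**Effect of the entry range.** Simulating selection on a screening score of 19-28, with rounding and the 30-point cap (assumed mean 24-25, SD 3-3.5, r 0.6-0.8), Visit 1 cuts residual variance beyond Visit 3 by 9-17%. The two-covariate model is 28-32% below the planned change score.

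**Power at n = 20/10.** Simulated with 60,000 normally distributed trials per row, no truncation, change SD 2. The lost degrees of freedom and chance covariate imbalance are included. The last column is the change in mean 90% CI width from adding Visit 1 to a model that already has Visit 3.

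| a/b/c | Planned change | Mean of V1, V3 as baseline | V3 covariate | V3 + V1 covariates | CI width, V1 added to V3 |
|---|---|---|---|---|---|
| 0.5 all | 62% | 79% | 78% | 81% | −4% |
| 0.7 all | 62% | 79% | 70% | 79% | −7% |
| 0.8 all | 62% | 79% | 66% | 77% | −9% |
| 0.70/0.70/0.65 | 62% | 73% | 69% | 73% | −3% |
| 0.80/0.80/0.75 | 62% | 71% | 66% | 70% | −3% |
| 0.80/0.80/0.70 | 62% | 62% | 66% | 65% | +1% |
| 0.85/0.80/0.70 | 62% | 57% | 66% | 64% | +2% |

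The level depends strongly on the assumed SD. The planned test has 91%, 62%, 29% and 9% power at change SDs of 1.5, 2, 2.5 and 3. At SD 2.5 the two-covariate model gives 48-49% with all correlations at 0.7-0.8, 39% at 0.80/0.80/0.75 and 32% at 0.85/0.80/0.70.

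**The case against.** **Visit 3 is the baseline by design.** Section 3.9.3 says so, and the synopsis and section 7.4.1 agree. Visit 3 follows the placebo run-in and Visit 1 precedes it. This stands: the plan is coherent, and the point concerns efficiency only.

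**Visit 1 may predict Visit 7 less well.** It falls 4-6 weeks before Day 0, so 16-18 weeks before Visit 7 against 12 for Visit 3, and section 3.9.1 allows screening to extend to 56 days. This also stands. It is why the gain is a range, and why a fixed average of the two visits is unsafe. A covariate lets the data set the weight.

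**Much of the gain needs only Visit 3 adjustment.** True. With all correlations at 0.5, Visit 3 alone takes power from 62% to 78%, and Visit 1 adds 3 points. At 0.8 the order reverses: 4 points, then 11.

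**The within-arm tests and the non-parametric option are not helped.** Correct. Visit 1 should stay out of the within-arm tests, where regression to the mean (about 0.02-0.1 point in the simulated populations) and practice would enter. These limits narrow the proposal but do not defeat it.

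**A stronger reading.** A reader might infer that the plan throws away a quarter of the available variance reduction. The documents do not support that. The 25% is the fall in change-score variance from averaging two equally correlated baselines, and the documents give no correlation. As a share of the reduction that two baselines offer, the loss among change scores is 50% at r = 0.6, 27% at 0.7, 14% at 0.8 and 6% at 0.9.

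**Conclusion.** The point holds as a missed efficiency in the between-arm primary test; the plan contains no error or contradiction here. In every case run, ANCOVA on both pre-randomisation scores gave a narrower 90% CI than the planned change-score t-test, by about 15% at best (all correlations 0.5) and 1-2% at worst (0.85/0.80/0.70). At a change SD of 2, power moves from about 62% to 77-81% under equal correlations of 0.5-0.8, and to about 64-73% where Visit 1 correlates 0.05-0.10 less with Visit 7. The part due to Visit 1 itself runs from slightly negative to a 9% shorter interval. All of this rests on assumed SDs and correlations, normal scores, full follow-up and no true difference. Dropout or a true difference would lower every power figure.

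**What to change.** For the between-arm MoCA test only, prespecify before unblinding a linear model for the Visit 7 score (or, equivalently, for the change) with treatment, Visit 3 MoCA and Visit 1 MoCA. Compare the 90% CI for the treatment difference with (-2, 2). With Visit 3 in the model the treatment effect is the same whether score or change is the outcome, so the margin keeps its meaning.

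- Keep the within-arm tests on change from Visit 3.
- Do not use the fixed mean of Visits 1 and 3 as baseline.
- State which screening score counts if screening is repeated, for example the one on which eligibility was based.
- Apply the normality check to the model residuals, and say what replaces the model if they fail it. The planned non-parametric test on change from Visit 3 could serve.

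The cost is SAP wording and two degrees of freedom relative to the planned t-test (28 to 26), with no new assessment. If Visit 1 turns out to add little, there is a slight loss against adjusting for Visit 3 alone. The same approach could be considered for orthostatic pressure (Visits 1, 2 and 3) and for the diary and PPBC (Visits 2 and 3). That extension is optional and no calculation supports it here.
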